5.0 DATA MANAGEMENT

The CRFs will be the primary data collection tool for the study. All data requested on the CRF must be recorded. All data will be entered into a REDCap study database (McMaster University) and double verified.

6.0 ETHICS AND DISSEMINATION

6.1 Research Ethics Approval

This protocol will be reviewed and approved by the University of Maryland Institutional Review Board (IRB) and the McMaster University Research Ethics Board (REB) prior to commencement of the study.

6.2 Consent

Any patients who are deemed to meet all eligibility criteria should be approached to discuss participation in the trial by someone on the study team who is knowledgeable about the trial. In order to obtain informed consent, study personnel should follow the below procedures:

- Present study information in a manner that is understandable to the potential participant.
- Discuss the study with the potential participant and answer any questions he or she asks.

- Allow the potential participant an opportunity to discuss participation with their family, friends, or family physician if desired.
- Confirm that the participant understands the risks and benefits of participating in the study and that their participation is voluntary.
- Complete and obtain signatures for informed consent form and obtain contact information from the participant.

6.3 Confidentiality

Information about study participants will be kept confidential and will be managed in accordance with the below rules:

- All study-related information will be stored securely.
- All study participant information will be stored in locked file cabinets and accessible only to study personnel.
- All CRFs will be identified only by a coded participant number and initials.
- All records that contain participant names, or other identifying information (e.g. consent forms and contact information forms), will be stored separately from the study records that are identified only by the coded participant number and initials.
- All databases will be password protected.

In the event that a participant revokes authorization to collect or use personal health information (PHI), the clinical site retains the ability to use all information collected prior to the revocation of participant authorization. For participants who have revoked authorization to collect or use PHI, attempts should be made to obtain permission to collect at least vital status (i.e. primary outcome data) at the end of their scheduled study period.

6.4 Protocol Amendments

Any amendments to the study protocol which may affect the conduct of the study, or the potential safety of or benefits to participants (e.g. changes to the study objectives, study design, sample size, or study procedures) will require a formal amendment to the protocol. Any protocol amendments will be approved by the Principal Investigators and will require approval by the University of Maryland IRB and the McMaster University REB. Administrative changes (e.g. minor corrections or clarifications that have no effect on the way the study is conducted) will not need to undergo a formal amendment process.

6.5 Adverse Event Reporting and Definitions

6.5.1 Adverse event

An AE is any symptom, sign, illness, or experience that develops or worsens in severity during the course of this study.

6.5.2 Serious adverse event

AEs are classified as serious or non-serious. A serious adverse event (SAE) is any AE that is any of the following:

- Fatal
- Life threatening
- Requires or prolongs hospital stay

- Results in persistent or significant disability or incapacity
- A congenital anomaly or birth defect
- An important medical event

All SAEs must be recorded and promptly submitted to the local IRB.

6.5.3 Unanticipated problems resulting in risk to participant or others

Any incident, experience, or outcome that meets all of the following criteria:

- Unexpected in nature, severity, or frequency (e.g. not described in study-related documents such as the ethics-approved protocol or consent form, etc.).
- Related or possibly related to participation in the research (i.e. possibly related means there is reasonable possibility that the incident experience, or outcome may have been caused by the procedures involved in the research).
- Suggests that the research places participants or others at greater risk of harm (including physical, psychological, economic, or social harm).

All unanticipated problems resulting in risk to participants or others must be recorded and promptly submitted to the local IRB.

6.5.4 Adverse drug reactions

An adverse drug reaction is an injury caused by taking a medication. All adverse drug reactions that are considered both serious and unexpected are to be reported to the US Food and Drug Administration (FDA) within the following time periods of the information becoming available: 1) within 7 days for events that are fatal or life-threatening and 2) within 15 days for all other events that are not fatal or life-threatening.

6.6 Dissemination Policy

Results from the study will be submitted for publication regardless of whether or not there are significant findings. Every attempt will be made to ensure that the amount of time between completion of data collection and release of study findings are minimized.

Table 1: Schedule of Events

Assessment	Visit 1: Screening & Baseline	Visit 2: 6 Weeks	Visit 3: 3 Months	Visit 4: 6 Months	Visit 5: 9 Months	Visit 6: 12 Months
Screening	•					
Serum Calcium Analysis	•*	•	•			
Informed Consent	•					
Randomization	•					
Collection of Baseline Data (Demographic, Serum Metabolic Panel, Fracture, & Surgical Data)	•					
Nutritional/Placebo Supplementation**	•	•	•			
Assessment of Clinical Fracture Healing (FIX-IT)		•	•	•	•	•
X-Rays of Tibia or Femur	•	•	•	•	•	•
Assessment of Radiographic Fracture Healing (RUST)		•	•	•	•	•
Serum Bone Marker Analysis (CTX & PINP)	•	•	•			
Assessment of Adherence to Supplementation		•	•			
Laboratory Serum 25(OH)D Analysis	•	•	•			
Assessment for AEs		•	•	•	•	•
Serum PTH Level Analysis	•	•	•			
Assessment of Fracture Healing Complications		•	•	•	•	•
*To be assessed as eligibility criteria **Must occur within 1 week of fracture						

Table 2: Primary Outcome Analysis

Objective	Hypothesis	Fracture Healing Outcome	Method of Analysis
To determine the effect of vitamin D₃ dose on fracture healing at 3 months	High doses of supplementation (loading or daily) will increase healing compared to low daily dose. Using high doses will rapidly increase the circulating vitamin D available during fracture callus formation.	1. FIXIT (Clinical)	Patients in the high loading dose & high daily dose groups will be combined for a 2:1 comparison against low daily dose group using an Independent t-test (alpha=0.20)*
		2. RUST (Radiographic)	
		3. PINP (Biologic)	
		4. CTX (Biologic)	
To determine the effect of vitamin D₃ frequency on fracture healing at 3 months	High loading dose increases healing compared to high daily dose. Loading doses will overcome medication adherence issues and increase circulating vitamin D even more rapidly than daily doses.	1. FIXIT (Clinical)	Comparisons between the high loading dose & high daily dose groups will be made using an Independent t-test (alpha=0.20)*
		2. RUST (Radiographic)	
		3. PINP (Biologic)	
		4. CTX (Biologic)	
To determine the effect of low amounts of vitamin D₃ supplementation on fracture healing at 3 months	Low daily dose will increase healing compared to placebo. While the low daily dose is not expected to increase circulating vitamin D as rapidly as the high dose strategies, this comparison will determine if rapid serum increases are necessary to improve fracture healing.	1. FIXIT (Clinical)	Comparisons between the low daily dose & placebo groups will be made using an Independent t-test (alpha=0.20)*
		2. RUST (Radiographic)	
		3. PINP (Biologic)	
		4. CTX (Biologic)	

*Using Phase II screening trial approach, comparisons are non-definitive and an increased alpha level has been adopted.

Table 3: Secondary Outcome Analysis

Objective	Hypothesis	Fracture Healing Outcome	Method of Analysis
To determine if 25(OH)D serum levels are associated with fracture healing at 3 months	There will be an association between fracture healing and: 1) patients' enrolment serum 25(OH)D, 2) their change in 25(OH)D from enrolment to 3 months, 3) their 25(OH)D level at 3 months	1. FIXIT (Clinical)	Associations will be quantified using Univariate Analysis (alpha=0.20)*.
		2. RUST (Radiographic)	
		3. PINP (Biologic)	
		4. CTX (Biologic)	

*Using Phase II screening trial approach, comparisons are non-definitive and an increased alpha level has been adopted.

[figure not shown]
[figure not shown]
[figure not shown]
Table 4: Other Secondary Outcomes Analysis

Objective	Hypothesis	Outcome	Method of Analysis
Supplementation adherence	Daily vitamin D ₃ adherence will be <80% and loading dose vitamin D ₃ adherence will be >95%	Self-report	Summary statistics of means and confidence interval.
		Count of pills	
Participant safety	Adverse events will be rare across all 4 treatment groups.	Adverse event	Summary statistics of proportions.
	Re-operations for a composite of fracture healing complications will follow the same 3 hypotheses as fracture healing.	Re-operations for a composite of fracture healing complications	Summary statistics of proportions.
	Levels of serum calcium will be similar across the 4 treatment groups. Levels of serum calcium will be within normal reference ranges.	Serum Calcium	Summary statistics of means and confidence interval.
	Levels of serum PTH will be similar across the 4 treatment groups. Levels of serum PTH will be within normal reference ranges.	Serum PTH	Summary statistics of means and confidence interval.
Protocol adherence	Protocol adherence will be acceptable.	Complete follow-up assessments including x-rays and bloodwork	Summary statistics of proportions.

Figure 1: Femur Fracture

BONE: FEMUR (3)

Location: Diaphyseal segment (32)

- Types:
- A. Simple (32-A)
 - B. Wedge (32-B)
 - C. Complex (32-C)

[figure not shown]
[figure not shown]
[figure not shown]
[figure not shown]
[figure not shown]

Figure 2: Tibia Fracture

[figure not shown]
BONE: TIBIA/FIBULA (4)

Location:

Diaphyseal segment (42)

Types:
A. Simple (42-A)

B. Wedge (42-B)

C. Complex (42-C)

Figure 3: Unblinding of Personnel for Emergency Medical Management

1. In the event of a medical emergency that directly affects the health status of the participant, it may become necessary to unblind allocation status to determine the specific treatment the participant has received while enrolled in the study. A medical emergency is defined as an event which necessitates immediate attention regarding the treatment of a participant.
2. The clinical research coordinator should contact the principal investigator (or designee) and provide details of the medical emergency as soon as possible after the event. The principal investigator (or designee) is responsible for reviewing and approving all requests for unblinding. At no time will the participant's health be compromised or medical treatment delayed.
3. Once approved, the clinical research coordinator (or designee) will contact the unblinded Project Manager and request the participant's treatment allocation. The unblinded Project Manager will provide the clinical research coordinator with the participant's treatment allocation. This information is to be provided by telephone. No information regarding treatment allocation is to be sent via email or fax.
4. The unblinded personnel are not to unblind the principal investigator or any blinded members of the study team unless deemed necessary by the principal investigator.
5. Study personnel must keep all information related to the individual unblinding cases confidential.
6. All cases of unblinding must be documented, including: study ID, date of unblinding, parties unblinded, and reason for unblinding.

Figure 4: Retention Strategies

1) We will exclude individuals who are likely to present problems with follow-up (see exclusion criteria).

2) At the time of randomization, as well as their own address and phone number, each participant will provide the name and address of their primary care physician, and the name, address and phone number of 3 people at different addresses with whom the participants does not live who are likely to be aware of the participant's whereabouts. The clinical research coordinator will confirm that these numbers are accurate prior to the participant's discharge from hospital.

3) Participants will receive reminders for upcoming clinic visits from local study personnel.

4) Follow-up schedules will coincide with normal surgical fracture clinic visits.

5) Study personnel will contact participants no less frequently than once every 3 months to maintain contact and obtain information about any planned change in residence.

Sprague et al⁴¹

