3.7.3 Other secondary outcomes

The other secondary outcomes will include assessing supplementation adherence between daily and loading doses, confirming participant safety as measured by AEs and serum levels of calcium and parathyroid hormone (PTH), and assessing protocol adherence (e.g. completion of outcome assessment and participant follow-up).

Adherence with vitamin D supplementation will be assessed by participant self-report, by counting the tablets for the daily doses at each follow-up, and by direct observation for the loading doses.

Participant safety will be assessed by AEs, defined as any symptom, sign, illness, or experience that develops or worsens in severity during the course of this study. Within the AEs collected, fracture healing complications will be identified, and will include nonunion (defined as failure of the fracture to progress towards healing for 2 consecutive months and at least 6 months post-fracture), delayed union (defined as a failure of progression of fracture healing beyond the expected median healing time of 4 months with pain at the fracture site), hardware failure (defined as broken or bent nail or locking screw),³³ wound healing problems (previously published criteria by Anglen 2005), and infection (superficial and deep as defined by Centers for Disease Control and Prevention (CDC) criteria). Wound healing problems and infection are a part of the composite fracture healing complication outcome because previous animal and infectious disease clinical research has suggested that vitamin D can improve wound healing and reduce infections.³⁴⁻³⁷ In addition to AEs, serum levels of calcium and PTH will be monitored and we will record results of the participants' pre-operative metabolic profile. These data will be used to understand the baseline metabolic health of the participants and will be used as needed in the event of suspected AEs.

Participant adherence with the protocol will be assessed by monitoring the completion of outcome measures, including clinic assessments (FIX-IT), radiographs (RUST), and blood work (CTX, PINP, 25(OH)D, calcium, and PTH), documentation of AEs and re-operations, and completion of follow-up to 12 months.

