4.0 STATISTICAL PLAN

4.1 Sample Size Determination

This trial will use a phase II randomized screening design to facilitate non-definitive comparisons of three vitamin D₃ dosing regimens. Using the principles outlined by Rubinstein et al, the statistical parameters have been carefully chosen to ensure a reasonable sample size and meaningful results.⁴² Consistent with previous recommendations, an α and β of 0.20 was chosen with a target mean difference of 17-20%, depending on the fracture healing measure. There will be no adjustments for multiple testing given the exploratory nature of the study design.

Based on the original instrument development and validation in tibia and femur fracture patients, it is expected that the low dose and control groups will have a mean 3-month FIX-IT score of 8 (standard deviation (SD) 3).¹⁸ Assuming the high dose groups will achieve a mean 2 point increase (17% mean difference), 21 patients are required in each group. The same sample size requirements will be applied for comparisons using the RUST instrument based on similar assumptions and recent literature (2 point mean difference, 8 vs. 6, SD 3).¹⁹⁻²² Clinically important changes in the PINP and CTX markers are unknown; however, in a previous study of tibia fracture healing, Veitch et al observed concentrations of both bone turnover markers approximately 100% greater than baseline values.⁴³ Given the large changes observed in these bone turnover markers, the same criteria will be applied for identifying a potentially clinically beneficial regimen and remain powered to detect a mean difference of 20% (SD 30%). Finally, the sample size will be increased to account for a 10% loss to follow-up, for a total enrolment of 24 patients per allocation group (96 total).

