4.2.3 Other Secondary Outcomes

All other secondary outcomes will be presented using point estimates and appropriate measures of variance to describe supplementation adherence, participant safety, and key aspects of participant compliance with the protocol (**Table 4**). Supplement adherence will be summarized using means and 95% confidence intervals for participant self-reporting and the mean cumulative dose taken at 3 months. The incidence of AEs and re-operations for fracture healing complications in each group will be described with counts and proportions. Serum levels of calcium and PTH will be summarized using means and 95% CIs. Participant compliance with the protocol will be summarized descriptively with counts and proportions.

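### Calcium and PTH are hypothesised to be similar across arms, but no between-arm difference is planned, and separate arm means with 95% CIs cannot support that conclusion at 21 to 24 per arm

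*Combined protocol and SAP*

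**What the plan says.** Table 4 (Other Secondary Outcomes Analysis, participant safety rows) gives two hypotheses for each marker. The first compares arms: "Levels of serum calcium will be similar across the 4 treatment groups" and "Levels of serum PTH will be similar across the 4 treatment groups". The second concerns level; for calcium it reads "Levels of serum calcium will be within normal reference ranges". The method for both markers is "Summary statistics of means and confidence interval".

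Section 4.2.3 agrees: "Serum levels of calcium and PTH will be summarized using means and 95% CIs". Its general rule is that "All other secondary outcomes will be presented using point estimates and appropriate measures of variance". Neither place gives a between-arm difference, an interval for one, a test, a margin or a rule for reading similarity, and none appears elsewhere.

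Section 3.7.3 makes calcium and PTH part of the confirmation of participant safety. Table 1 schedules both at enrolment, 6 weeks and 3 months. By contrast, Section 4.2.1 gives the fracture-healing hypotheses explicit two-group t-tests at alpha 0.20.

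**The concern.** The hypothesis is comparative but the analysis is not. Four arm means, each with its own interval, do not state how far an active arm may differ from placebo. A reader who has to judge similarity from them must supply a rule after seeing the results. The natural ones (intervals overlap, no significant difference) turn imprecision into reassurance.

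Section 3.5.4 names hypercalcemia as the theoretical harm, and the trial is meant to inform a Phase III dosing trial. A statement that calcium and PTH were similar would be carried into that design. It should rest on an estimated difference and its limits.

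**Working it through.** **Inputs from the plan (Section 4.1).** Difference 2 points, SD 3, alpha 0.20, power 0.80, 21 per group, 24 per group after 10% loss, 96 in total.

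**Reproducing the plan's figure.** Two-sided: n = 2(z0.90 + z0.80)² × (3/2)² = 2(1.282 + 0.842)² × 2.25 = 20.3, so 21. Then 21/0.9 = 23.3, so 24, and 4 × 24 = 96. The plan's figures reproduce. It states no size, power or precision for calcium or PTH.

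**Assumptions.** Normal data, equal SDs, results in SD units, n = 21 (evaluable) and 24 (enrolled) per arm. The 0.5-SD shift is illustrative. That means will be shown by arm is inferred from the wording of the hypothesis. The figures are symmetric, so they hold for a rise or a fall; the documents give no harmful direction for PTH.

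**Precision.**
- One arm: t(0.975, n−1)/√n = 2.086/√21 = 0.46 SD; 2.069/√24 = 0.42 SD.
- Difference: t(0.975, 2n−2) × √(2/n) = 2.021 × 0.309 = 0.62 SD; 2.013 × 0.289 = 0.58 SD.
- Two arm intervals separate only if the observed difference exceeds the sum of their half-widths, about 0.91 SD (n = 21) or 0.84 SD (n = 24). That is well beyond the 0.62 or 0.58 SD at which the interval for the difference excludes zero.

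**Chance that a true 0.5-SD shift in one active arm is not flagged, by reading rule.** Overlap and mean-inside figures are simulated; the other two rows use the noncentral t.

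| Reading rule | n = 21 | n = 24 |
|---|---|---|
| The two separate 95% CIs overlap | 0.89 | 0.87 |
| 95% CI for the difference includes 0 | 0.65 | 0.60 |
| Placebo mean lies inside the active arm's 95% CI | 0.44 | 0.39 |
| Two-sided test at alpha 0.20 not significant | 0.37 | 0.33 |

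At 0.75 SD the two intervals still overlap in 0.68 (n = 21) or 0.61 (n = 24) of trials.

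**What a reported difference would show.** With a true 0.5-SD shift, the typical upper limit is 0.5 + 0.62 = 1.12 SD (n = 21) or 0.5 + 0.58 = 1.08 SD (n = 24). The reader would see that a large difference had not been excluded.

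**Scale in mg/dL.** If the calcium SD is 0.3 to 0.5 mg/dL (assumption), the unadjusted half-width for the difference is 0.19 to 0.31 (n = 21) or 0.17 to 0.29 (n = 24). Adjusting for an enrolment value correlated 0.5 with follow-up (assumption) multiplies it by √(1 − 0.25) = 0.866, giving 0.16 to 0.27 or 0.15 to 0.25.

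**Limits of a formal margin.** With no true difference, the chance that the upper limit of an unadjusted 95% CI falls below 0.5 SD is 0.35 (n = 21) or 0.40 (n = 24) per comparison. With the adjustment above it is about 0.45 or 0.50. Excluding 0.5 SD with 80% power at one-sided 0.025 needs 2(1.960 + 0.842)²/0.5² = 62.8, so 63 per arm.

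**The case against.** The strongest reply is that the documents contain no overlap rule and do not say that a verdict will be issued. A reader might infer that the plan judges similarity by overlapping intervals and would therefore usually call a 0.5-SD shift similar. The text does not support that. The 87% to 89% figure belongs to one possible reading, and under the two less strict readings the shift is missed less than half the time. What stands is that the plan fixes no reading at all.

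A reader might also infer that the enrolment values are discarded. They are not: Table 1 collects them, and Section 4.2.3 does not restrict its summaries by visit. The plan simply states no use of them in a comparison.

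Descriptive reporting does suit a trial whose analyses are all exploratory (Section 4.2), and other Table 4 rows likewise pair an expectation with summary statistics. Arm means, intervals and group sizes would let a reader rebuild the unadjusted difference, though not the adjusted one. This argues against demanding a formal non-inferiority test, and that part is accepted. It does not justify a similarity conclusion without an estimated difference.

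Finally, hypercalcemia is an individual event, covered by serial calcium checks, adverse event counts and the reference-range hypothesis. That is correct and limits the stakes. Those safeguards address individual values and levels, however. A shift in an arm's mean that stays within the normal range would escape them, and that is what the between-arm hypothesis concerns.

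**Conclusion.** The point holds as a mismatch between hypothesis and analysis. The plan states between-arm similarity for calcium and PTH, specifies no between-arm estimate and gives no reading rule. At 21 to 24 per arm, separate summaries cannot establish similarity: the chance of missing a 0.5-SD shift runs from 33% to 89% depending on the rule chosen, and is 60% or more under the two 95%-level interval readings (overlap, or the difference interval including zero).

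The size rests on normality, equal SDs and an illustrative 0.5-SD benchmark. Nothing in the documents says that such a shift is clinically relevant. A compulsory margin does not follow either: near 0.5 SD it would often return 'not established' when there is no true difference. The weight is moderate, because the trial is exploratory and individual calcium monitoring is separate.

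**What to change.** In Section 4.2.3 and the calcium and PTH rows of Table 4:

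- At 6 weeks and at 3 months, estimate each active arm minus placebo difference in calcium and in PTH, adjusted for the enrolment value, with a 95% CI.
- Keep the arm means and their intervals as descriptive output.
- Replace the similarity verdict with a statement of which differences each interval does and does not exclude.
- Treat a calcium margin as optional. If the investigators want one, they should fix it in mg/dL before unblinding and acknowledge that, at this size, a margin near 0.5 SD would often not be met even with no true difference.

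The cost is a few lines of wording and one regression per marker and visit, on data already scheduled in Table 1. The downside is a little more analysis and a safety statement that may read less favourably. Individual hypercalcemia monitoring and the reference-range hypothesis are unaffected.
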